5.5 Premature Termination or Suspension of Study

This study may be temporarily suspended or prematurely terminated if there is sufficient reasonable cause. If the study is prematurely terminated or suspended, the PI will promptly inform the IRB and will provide the reason(s) for the termination or suspension.

Circumstances that may warrant termination or suspension include, but are not limited to:

- Determination of unexpected, significant, or unacceptable risk to participants
- Demonstration of efficacy that would warrant stopping
- Insufficient compliance to protocol requirements
- Data that are not sufficiently complete and/or evaluable
- Determination of futility

Study may resume once concerns about safety, protocol compliance, data quality are addressed and satisfy the sponsor, IRB and/or FDA.

6 Study Device Intervention

6.1 Study Device Description

tDCS is a device that delivers weak electrical current (2.0 mA) through sponge electrodes placed on the scalp. The main components are:

- **1x1 Mini CT tDCS device:** The device is powered by 9-volt (V) rechargeable batteries. The device can be easily operated, with a user-friendly large-button keypad interface. The device allows strict dose control and usage control, employing a one-time use code provided by the study technician to unlock the device for each stimulation session. The high sensitivity of the device to any changes allows us to monitor in real time the contact quality between the surface of the electrode and the skin ensuring safety and high quality of the delivered stimulation.
 - **tDCS Headset:** The headset will be used to standardize and simplify the electrode placement. The headset uses two electrodes: the anode electrode and the cathode electrode. An electrode montage targeting the left frontotemporal lobe (anode over F7 and cathode over O1) electrode montage will be used. The headset connects to the tDCS device with two wires (anode and cathode).
- **Sponge electrodes:** The electrodes are square (5 x 5 cm²) pre-saturated saline sponge electrodes packaged for single use equipped with snaps to fasten the sponges to the headset. The participant will be only required to open the package and snap the sponge onto the headset. The use of pre-moistened, single-use electrodes avoids the possibility of over-saturating the sponge as this can saturate the hair, affecting the spread and the direction of the current flow.

tDCS is a non-significant risk device because it is:

1. not intended as an implant.
2. it is not purported or represented to be for use supporting or sustaining human life.
3. it is not for a use of substantial importance in diagnosing, curing, mitigating, or treating disease or otherwise prevent impairment of human health and does not present a potential for serious risk to the health, safety, or welfare of a subject. tDCS has an established record of safety and tolerability for use from trials in a range of neurological and psychiatric conditions^{58 59}, and including the specific remotely supervised and remote use as proposed for this study^{60 61}. It has NSR designation for our trials specifically using the proposed procedures in participants with MS^{62 63 64 65 66 67 68} as well as for use as an NYU Langone Health approval as innovative care for our tDCS clinical service program⁶⁹.
4. it does not otherwise present a potential for serious risk to the health, safety, or welfare of a subject

6.1.1 Acquisition

The devices used in the NYU Langone RS-tDCS research program are manufactured by Soterix Medical Inc. and owned by NYULH.

6.1.2 Product Storage and Stability

Devices, when not allocated to participants, are stored in-house in a locked room. Device allocation notes including device serial number and device unlock codes will be stored for reference.

6.1.3 Device Programming

To ensure blinding, devices will be pre-programmed in advance by an independent staff member, who will not take part in the treatment and assessment⁷⁰⁻⁷². The device is programmed to ramp up to 2.0 mA (for 30 seconds), provide constant current throughout session (29 minutes), and then ramp down (for 30 seconds) at the end.

6.1.4 Dosing and Administration

The tDCS device will deliver each session 2.0 mA for 30 minutes over the left frontotemporal lobe with focus on the inferior frontal gyrus (IFG). Participants will receive 20 intervention sessions over the course of this study on weekdays (M-F).

Study technicians are always live with participants via Zoom when initiating and delivering the treatment and can address any issues that arise during treatment. Study technicians will direct headset placement remotely. The tDCS device can only operate if: **1)** the headset is correctly placed for adequate connection, and **2)** the study technician provides a session code that unlocks the device for a one-time only 30-minute period of use.

If the device loses adequate electrode contact for any reason, the device will automatically discontinue the session. The session can only be reestablished if another unlock code is provided by the study technician.

Specific stop criteria are outlined for treatment administration. Should any stop criteria be met at any point in administration of treatment, the participant will not undergo any further treatments and will be asked to return the study equipment. If the participant wishes to discontinue a session, they may press the "abort" key at any time, which ramps down and stops the stimulation current within 30 seconds.

6.1.5 Route of Administration

tDCS is administered through a paired of sponge electrodes placed on the scalp using the headset. The device allows strict usage control, employing a one-time use code provided by the study technician to unlock the device for each stimulation session.

6.1.6 Duration of Intervention

Participants will complete 20 sessions of active RS-tDCS over the course of approximately 4 weeks. The tDCS will be programmed to deliver 30 minutes of stimulation.

6.1.7 Device Specific Considerations

- Device size: Height 7.2 in; Width 3.6 in; Depth 1.2 in
- Device model: Model 1601
- Device settings and programming: Double-blind option: Sham (ON/OFF), Secure administrator mode to program sessions, storage of data and codes of 250 sessions; SMARTscan to provide continuous visual indication of electrode quality during stimulation

6.2 Study Device Accountability Procedures

The device accountability and inventory log will be used to log device-use including subject ID, date shipped, dates used, session technician, and date returned.

7 Study Behavioral Intervention

7.1.1 Word Naming Practice

Each tDCS session will include simultaneous word naming practice via live video visit supervision with the trained tDCS clinician. tDCS clinicians for this study will be experienced psychometricians with master's level training and

supervised by speech and language pathologist, [name]. Consistent with the protocol outlined by Flurie et al, 2020, study participants, with caregiver support, will select 100 treatment items of personal relevance (i.e., high familiarity and frequency) from a fixed list of 220 possible items representing everyday objects (nouns) and actions (verbs) (e.g., hat, toothbrush, book, supermarket, coffee, cooking, reading)³³. Unselected items from the original list of 220 items served as the control word naming list. Baseline performance will dictate the number of words reviewed per treatment session to reduce the burden on participants.

During each RS-tDCS session, once the stimulation has been activated the tDCS clinician will guide the participant in the word naming practice. Following the procedures of Henry et al. (2019), participants will be presented with photos of target items (via Zoom) and prompted to verbally produce the names of the pictures (common nouns and verbs) with the support of a word naming cueing hierarchy aimed at facilitating word retrieval through self-cueing³⁵. Participants will be guided as needed through the prompting of semantic, orthographic, and phonological information about the target word. All cues within the hierarchy will be presented to the participant for each item whether they correctly identify the stimulus or not. This is in effort to reinforce lexical retrieval of the target stimuli. The word naming approach is consistent across all participants in the study and described in detail below and outlined in Table 1.

- Semantic Self-Cue
 - When a target picture is presented for naming, the participant will first be instructed to generate semantic features/conceptual information using a fixed set of questions (e.g., “Where do you find it?” “What is it used for?”). At this stage, participants are also asked to provide any personal historical information about the target (e.g., “I drink this every morning”).
- Orthographic Self-Cue
 - Next, participants are asked about any orthographic (written) information they might have about the word (i.e., whether they can write the word or the first letter of the word).
- Phonemic Self-Cue
 - Participants are then asked to provide phonological or sound-based information about the word (e.g., the initial sound). If the participant cannot retrieve any aspect of the orthographic (written) or phonological (sound form) of the target, they are given the first letter of the target (e.g., for “coffee” they would be given the letter “c”) and will be asked to produce the corresponding sound of the letter. If the participant cannot produce the corresponding sound then the technician will provide it.
- Oral Reading
 - Should the participant still be unable to name the word, the written form will be provided for oral reading. If the participant has difficulty reading the target word, then the spoken form will be given.
- Written and Spoken Repetition
 - After these steps, the spoken and written forms for the target is named three times.
- Yes/No Questions
 - Then yes/no questions are given to the participant (e.g., “Do you use this in your hair?”).
- Recall
 - Finally, participants are asked to provide two semantic characteristics about the target (e.g., for coffee, participant might say, “you drink it”) and attempt to name and write the word.
 - Regardless of whether the participant is able to name the target at any step, they continued with the remaining steps (excluding the yes/no questions).

Table 1. Word Naming Practice Cues

Training Step	Procedure	Instructions
----------------------	------------------	---------------------

1. Semantic self-cue	Picture presented; patient prompted for semantic information and/or autobiographical information	What can you tell me about it? (Where do you find it? What is it used for? What is it made of?)
2. Orthographic self-cue	Prompt written form or first letter of word	Can you write the word? Can you write the first letter?
3. Phonemic self-cue	Prompt initial phoneme	What sound does that letter make? What is the first sound of the word?
4. Oral reading	If item not named, provide written form and participant reads aloud	Here is the word. Can you read it?
5. Written and spoken repetition	Participant writes and says the word three times	Now write and say the word (three times).
6. Yes/no question	Provide participants with yes/no questions.	E.g., Is it sweet? Can you buy it at the supermarket?
8. Recall	Participant provides two semantic features and writes and says the word.	Now tell me two important things about this item. What is this called? Can you write it?

Adapted from Henry et al., 2019.

7.1.2 Administration of Intervention

Participants may receive a laptop computer with access to Zoom if they do not already have the necessary resources to virtually meet with a study technician. All study procedures requiring contact with a study clinician (RS-tDCS, language assessment, and word naming practice) will be conducted using this laptop and Zoom connection.

8 Study Procedures and Schedule

8.1 Study Procedures

- Pre-screening:
 - Diagnosis of PPA and tDCS eligibility will be confirmed via medical records.

After subjects provide written informed consent, the following research procedures will take place over approximately 2 weeks:

- Baseline Visit:
 - Following procedures for our validated protocol^{37–41,43–47}, participants will first receive training on the use of the tDCS device and headset.
 - Participants will undergo a 90-second tDCS tolerability test to ensure the stimulation is tolerable. The participant will be given a one-time use code to initiate the stimulation, the tDCS device will

- ramp up to its target stimulation intensity (2.0mA) and after 90 seconds, participants will be instructed to press “0” to stop the test. Participants are free to stop the test at any time before the 90 seconds. Participants will then be instructed to remove the headset. Participants who cannot tolerate 2.0 mA will be considered a screen failure.
- Participants will complete self-report questionnaires about their language use and daily functioning through REDCap survey function (see assessments section 8.2 below).
 - Participants will identify a list of high frequency common nouns and verbs that they use in their daily life. This list of words will then be utilized to make the trained and untrained stimuli lists.
 - For exploratory research, participants will complete cognitive measures (QAB, BNT, COWAT).
 - tDCS Session 1:
 - Participants will have their first 30-minute remote session of 2.0mA active tDCS combined with word naming practice. Participants will be presented with the list of common nouns and verbs previously identified and practice verbally identifying those words from pictures with the help of a lexica retrieval cuing hierarchy. At each treatment session, participants will complete brief adverse event reports before and after each session. Once the study technician visually confirms correct headset placement and participants confirms adequate contact quality (moderate or good), the technician will provide the participant with a one-time use unlock code to enter into their tDCS device. The participant enters the code when ready to initiate the stimulation. During each stimulation session participants will listen to a guided mindfulness meditation audio track on the study provided laptop computer.
 - Remotely-Supervised tDCS Sessions 2-20:
 - Over the next 4 weeks, participants will complete the remaining daily RS-tDCS + word naming practice as described above for session 1.
 - tDCS session 20 & Treatment-end: After completing the final tDCS session, participants will repeat the baseline self-report questionnaires and language assessment. Participants will be asked to return the equipment via Fedex using a prepaid return label.

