Description of Study Procedure	
tDCS is noninvasive brain stimulation device that modulate brain activity delivering a low-intensity electrical current (2.0 mA) through scalp sponge electrodes. The device is preprogrammed to ramp up to 2.0 mA (for 30 seconds), provide constant current throughout session (29 minutes), and then ramp down (for 30 seconds) at the end.
 
Treatment is via telehealth visits, remotely and monitored through live videoconference using the established remotely supervised (RS) tDCS procedure.
 
During the stimulation period, participants will engage in a picture naming exercise during the stimulation as guided by the study tDCS clinicians.

Key Procedures	Active tDCS with simultaneous word naming practice.

Statistical Analysis	
To measure feasibility, individuals will be categorized as “compliant” based on the percentage of study visits completed (16/20). Compliance with the interventions will be assessed by summarizing the distributions of numbers and proportions of completed sessions.
 
Preliminary efficacy will be measured by performance at baseline and study end across study measures (QAB, BNT, COWAT, self-report questionnaires). Change in scores, indicating change following intervention, will be calculated for each compliant participant (defined as above).

----------------------	---

SCHEMATIC OF STUDY DESIGN

Prior to
Enrollment

Confirm eligibility criteria via medical records and self-report;
Obtain informed consent

Baseline
Day 1

Self-report questionnaires (ACOM, SAQOL-39, PROMIS Social Roles and Activities, PROMIS Global Health)
Baseline Language Assessment (Trained and Untrained Words, QAB, BNT, COWAT)
tDCS training and tolerability testing
RS-tDCS + word naming practice

Intervention
Day 2 – Day 19

5 Days a week: **RS-tDCS + word naming practice**

Final Treatment Day
Day 20

RS-tDCS + word naming practice
Post-intervention assessment
Post-stimulation language assessment (Trained and Untrained Words, QAB, BNT, COWAT)
Self-report questionnaires (ACOM, SAQOL-39, PROMIS Social Roles and Activities, PROMIS Global Health)

1 Key Roles

[name], Principal Investigator
NYU Langone Health — Neurology
[name]
[contact]
[contact]

2 Introduction, Background Information and Scientific Rationale

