3.1 Primary Objective

To evaluate the feasibility of an RS-tDCS service and concurrent word naming practice.

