4.1 Description of Study Design

This study will recruit n=30 PPA patients to receive 20x30 min sessions of active 2.0mA tDCS, combined with simultaneous word naming practice over a 4-week period.

All participants will have a remote consent/research screening visit, baseline visit, 20 tDCS treatment visits, and post-treatment assessment. All visits will be completed remotely using Zoom.

This will be a single site study at NYU Langone Health and will take place over a 2-year period.

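### Section 8.1 orders a guided meditation track during every stimulation session, in the same 30 minutes that the plan gives to word naming practice

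*Combined protocol and SAP*

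**What the plan says.** The Session 1 entry in Section 8.1 opens with naming as the paired activity: "Participants will have their first 30-minute remote session of 2.0mA active tDCS combined with word naming practice". It goes through adverse event reports, headset checks and the unlock code, then closes with a different activity: "During each stimulation session participants will listen to a guided mindfulness meditation audio track on the study provided laptop computer". For sessions 2 to 20, the same section says that "participants will complete the remaining daily RS-tDCS + word naming practice as described above for session 1".

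Other parts of the protocol describe naming alone as the concurrent task:

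- Protocol Summary, Description of Study Procedure: "participants will engage in a picture naming exercise during the stimulation as guided by the study tDCS clinicians".
- Section 4.1: "20x30 min sessions of active 2.0mA tDCS, combined with simultaneous word naming practice over a 4-week period".
- Section 7.1.1: "once the stimulation has been activated the tDCS clinician will guide the participant in the word naming practice". The same section adds: "The word naming approach is consistent across all participants in the study".

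The primary objective in Section 3.1 is worded to match: "To evaluate the feasibility of an RS-tDCS service and concurrent word naming practice".

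**The concern.** One entry in the procedures section gives two activities for one stimulation period. A technician working from Section 8.1 could not satisfy both. If the track is played, it either displaces naming or runs underneath a task that requires people with aphasia to listen to prompts, speak and write.

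The study has a single arm. If meditation were delivered, its contribution to change in language scores or self-reported quality of life could not be separated from that of tDCS with naming. Sections 3.2 and 10.3 intend those changes to inform the power and sample size calculations for a later controlled trial. The feasibility result would also describe a different package from the one in the primary objective.

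If staff ignore the sentence, they depart from the written procedure at every session, and Section 14.3 counts any noncompliance with the protocol as a deviation.

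**Working it through.** No statistical calculation applies, and the plan states no figure on this point. The check is whether the two instructions occupy the same time, and whether any text reconciles them.

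**Step 1: the time available.** Section 6.1.3 programs a 30-second ramp-up, 29 minutes of constant current and a 30-second ramp-down: 0.5 + 29 + 0.5 = 30 minutes. Section 7.1.1 starts naming when stimulation starts. The meditation sentence places the track within the stimulation session. Both therefore claim the same 30 minutes.

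**Step 2: a possible separate slot.** The section on duration of participation gives Session 1 a further 15 minutes and assigns them to naming. Section 8.3 lists 45 minutes for each tDCS visit, and 45 − 30 = 15. Even if those 15 minutes were open at later visits, they would lie outside stimulation, where the sentence does not put the track. No section divides the stimulation period between the two activities.

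**Step 3: whether both could be done at once.** Table 1 in Section 7.1.1 has seven rows, numbered 1 to 6 and 8.

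- All seven give a prompt for the clinician to deliver.
- Five call for speech (rows 1, 3, 4, 5 and 8; row 4 only if the item has not been named).
- Three call for writing (rows 2, 5 and 8).
- Row 6 is a yes/no answer and is not counted as speech here.

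The exact counts matter little. The task is a continuous exchange with a clinician over Zoom, which is not compatible with listening to a guided audio track.

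**Step 4: other mentions.** Meditation does not appear in the objectives (Section 3), the behavioral intervention (Section 7), the assessments (Section 8.2), the study schedule (Section 8.3) or the Schedule of Events (Section 19). It has no script, purpose or data item.

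**Step 5: reach.** Because the later sessions follow the Session 1 procedure, the sentence covers 20 × 30 = 600 minutes of planned stimulation per participant and at most 30 × 20 = 600 planned sessions. These figures measure planned exposure to an ambiguous instruction, not an effect. The second is also an upper limit: the 30 are counted at consent, and participants who fail the later tolerability test are screen failures.

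**The case against.** The strongest reply is that nobody would act on the sentence. A clinician leads naming live in every session, the same entry orders naming, and the carry-forward text for later sessions mentions naming and not meditation. Section 7 is the fuller specification of the behavioral intervention, and nothing equips staff to deliver meditation. This stands as an argument about consequence, and it is why the practical effect is probably small. It does not remove the conflict from the text.

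A narrower reply is that Section 8.1 says only that tDCS is combined with naming, which might allow the two activities in sequence. The Protocol Summary and Sections 4.1 and 7.1.1 close that route by placing naming during stimulation.

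Some stronger readings are tempting but unsupported:

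- A reader might infer that Section 8.1 governs and overrides Section 7. The protocol does not rank the two.
- A reader might infer that every other description excludes any second activity, or that every one specifies clinician guidance. None says that naming is the only activity. Section 4.1 and Section 8.3.5 say that practice is simultaneous without mentioning who leads it; clinician guidance comes from the Protocol Summary and Section 7.1.1.
- A reader might treat the sentence as proven leftover text. The references to a sham arm in Section 2.4.1 and to blinding in Section 6.1.3, both out of place in a single-arm open-label study, make that plausible, but it remains an inference. The laptop wording is weak evidence, because Section 7.1.2 itself first makes a study laptop conditional and then runs all clinician contact on it.

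**Conclusion.** The plan is wrong as written: Section 8.1 contradicts itself and conflicts with the Protocol Summary, Section 4.1 and Section 7.1.1 on what participants do during stimulation. This conclusion rests on the text alone and is secure.

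The consequence is conditional. If the sentence is followed, an undeclared co-intervention competes with naming, and neither the completed sessions nor the pre-post changes describe the intervention named in the primary objective. If it is ignored, as is more likely given how consistently naming is ordered elsewhere, the effect on results is small.

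A reader might infer that the primary endpoint fails or that all planned sessions are compromised. The documents do not support that: the 16-of-20 threshold counts sessions completed, the target of 30 does not depend on session content, and nothing shows that the track is or would be played. The point should be corrected, but it does not threaten the study's viability.

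**What to change.** Delete the meditation sentence from the Session 1 entry in Section 8.1, so that word naming practice is the only concurrent activity in sessions 1 to 20. Nothing else needs to change for this point, because the other sections already describe naming.

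The cost is one deleted sentence in an amendment, with the IRB review that Section 13.2 requires for any protocol change. It adds no visits, procedures, assessments or participants.

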5.2 Duration of Study Participation

Study participation will last approximately 1 month and will include:

- Remote consent (20 minutes), with participant provided as much time as they need to review consent form. Once consented, participant will be scheduled for telehealth research screening. The screening will be scheduled based on participant and study/physician availability, which can occur on the same day as consent and anticipated to be within one week of consent.
- Baseline speech and language assessment & tDCS Session 1 (approximately 3 hours: 20 minutes to orient to device, 1.5 hour assessments, 30 minute tDCS session, 15 additional minutes of word naming practice).
- tDCS treatment sessions (20 x 30 min session over 4 weeks)
- tDCS Session 20 & Treatment-end (2 hours)

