8.3.3 Baseline Visit (visit 1)

- Baseline language assessment (1.5 hours)
- Self-report questionnaires (20 minutes)

8.3.4 tDCS Session 1 (Visit 2)

- Train participant to use tDCS device (20 minutes)
- Perform tDCS tolerability test (2 minutes)
- Complete first remotely-supervised tDCS session + language skills practice (45 minutes)

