8.3.5 Remotely-Supervised tDCS sessions 2-19 (Visits 3-20)

- 20x30 minutes of active tDCS with simultaneous language skills practice (45 minutes)
- AE reporting

8.3.6 tDCS Session 20 & Treatment-end Visit (Visit 21)

- Participants will complete tDCS and word naming practice session 20 (45 minutes)
- Post-stimulation language assessment (1.5 hours)
Equipment return

9 Assessment of Safety

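### The only post-treatment language test follows session 20's practice in the same visit, so the trained-word change mixes same-session rehearsal with lasting gain

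*Combined protocol and SAP*

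**What the plan says.** Treatment end is described consistently. Section 8.1 gives the order: "After completing the final tDCS session, participants will repeat the baseline self-report questionnaires and language assessment". Section 8.3.6 (Visit 21) lists "Participants will complete tDCS and word naming practice session 20 (45 minutes" and then "Post-stimulation language assessment (1.5 hours". The schematic puts both on Day 20, with the content "Post-stimulation language assessment (Trained and Untrained Words, QAB, BNT, COWAT". Section 5.2 (Duration of Study Participation) gives the two a single time slot: "tDCS Session 20 & Treatment-end (2 hours".

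Baseline testing always precedes session 1, but what comes before it varies:

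- Section 8.3.3 lists "Baseline language assessment (1.5 hours" and "Self-report questionnaires (20 minutes" in Visit 1. Section 8.3.4 leaves "Train participant to use tDCS device (20 minutes" and the 2-minute tolerability test to Visit 2.
- The schematic also lists training and tolerability testing after the baseline language assessment.
- Section 8.1 lists training, tolerability test, questionnaires and word selection ahead of the QAB, BNT and COWAT.

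No rest interval, separate test day or later follow-up appears, and the Schedule of Events stops at treatment end. Trained and untrained probes at treatment end are a secondary endpoint in the Protocol Summary. Section 10.2 compares them before and after treatment to judge whether the intervention improved scores. Section 10.3 intends the preliminary efficacy data to support sample size calculations for a controlled trial.

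**The concern.** The practice in 7.1.1 is intensive for each item: several self-cues, three written and spoken repetitions, then recall with naming and writing. The trained-word test in 8.2.2 is also picture naming. An item drilled in session 20 is therefore tested by a closely similar task later in the same visit. At baseline no item has had any practice session.

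The one post-treatment measurement thus cannot separate what a participant retains after four weeks from what was rehearsed within the last hour or two. Section 2.1 describes the treatment goal as prolonging the preservation of language function, and a score taken straight after drilling is not a clean measure of that. If the trained-word change is later used as a planning effect size, any short-lived component carries into the next trial's sample size.

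**Working it through.** The plan gives no figure for this effect, so the check compares the order of events, adds up the stated durations and illustrates the possible size.

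**1. Order of events.** At treatment end the sequence is stimulation and practice, then testing (8.1, 8.3.6, schematic). At baseline it is testing, then session 1 (8.1, 8.3.3 and 8.3.4, schematic). The difference holds in every version.

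**2. How many trained words are affected.** Section 7.1.1 sets the trained list at 100 of 220 items and lets baseline performance decide how many are reviewed per session. It gives no number. Only items actually reviewed in session 20 are rehearsed that day.

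- Illustrative assumption: 10 items reviewed, with a short-lived naming gain of 10 to 30 percentage points on them.
- Words added = 10 × 0.10 = 1, to 10 × 0.30 = 3, out of 100.
- Plausibility of larger counts: 50 items in a 45-minute session leaves 45 × 60 / 50 = 54 seconds per item, little for a multi-step cueing hierarchy in people with PPA. Ten items leaves 45 / 10 = 4.5 minutes each.

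Neither the item count nor the gain comes from the documents.

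**3. Scheduled activity before the language test** (durations from 8.3.3, 8.3.4 and 8.3.6).

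- Treatment end: 45 minutes, or 45 + 20 = 65 if the questionnaires come first.
- Baseline in the 8.1 order: 20 + 2 + 20 = 42 minutes, plus word selection, which has no stated time.
- Baseline in the 8.3.3 order: 0 minutes, or 20 if the questionnaires come first.
- Extra load at treatment end against 8.1: 45 − 42 = 3 to 65 − 42 = 23 minutes, less the time for word selection.
- Extra load against 8.3.3: 45 − 20 = 25 to 65 − 0 = 65 minutes, depending on where the questionnaires fall.

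**4. Visit length.** From 8.3.6, 45 + 90 = 135 minutes. With 20 minutes of questionnaires inside the visit it is 155. Section 5.2 allows 120, so the excess is 15 minutes (15 / 120 = 12.5%) or 35 minutes (35 / 120 = 29%). The stated 2 hours is matched only by 30 + 90 = 120, which drops the additional 15 minutes of practice that 5.2 itself counts for session 1.

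**The case against.** The strongest reply is that testing immediately after treatment is a recognisable choice, that session 20 is itself part of the intervention, and that no retention endpoint is planned: 10.4 defines the outcome as change at study end. The affected outcomes are exploratory, in an uncontrolled pilot of 30 people. After 19 earlier sessions on familiar words there may be little room for a further same-day gain. Section 2.1 also says that a single tDCS session produces no meaningful behavioural response.

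Much of this stands, and it limits the importance of the point. It does not remove it. The statement in 2.1 concerns stimulation, so it makes an acute stimulation effect less likely but says nothing about rehearsal of the tested words. Nothing in the plan says that the outcome is meant to be the state immediately after practice.

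Three stronger readings are tempting but not supported:

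- A reader might infer that the QAB, BNT and COWAT are taken fatigued and so biased downward. The documents say nothing about fatigue, and in the 8.1 order the baseline tests also follow at least 42 minutes of activity.
- A reader might infer that the whole trained list is freshly rehearsed and the gain is large. Section 7.1.1 gives no count per session.
- A reader might infer that a planned trained-minus-untrained analysis is biased upward. No such contrast is specified, and the Objective 2 methods in 10.4 do not mention the word probes. If the contrast were made, it would contain the rehearsal effect, since only trained items are practised. It would also be confounded because participants choose their own trained items, which reordering would not cure.

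**Conclusion.** The point holds in a limited form. Trained items practised in session 20 are tested the same day, while baseline precedes all practice, so the change in trained words mixes same-session rehearsal and possible acute stimulation with lasting change. Nothing elsewhere in the plan corrects this.

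Rehearsal would act upward on the practised items. Its size cannot be derived from the documents, and the 1 to 3 words per 100 rest wholly on the assumed 10 items and 10 to 30 point gain. No direction is established for the QAB, BNT or COWAT.

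The primary endpoint, completion of 16 of 20 sessions, is untouched. This is a cheap improvement to secondary and exploratory outcomes. The visit-length mismatch is a separate clerical inconsistency.

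**What to change.** In the schematic, 8.1 and 8.3.6, move the treatment-end language assessment to one of two places:

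- **The next weekday, before equipment return.** This keeps all 20 sessions and removes same-session rehearsal. It must precede return because 7.1.2 has assessments run on the study laptop where one is lent. Cost: one more remote contact, which a participant could miss.
- **Before session 20's stimulation and practice, in the same visit.** No extra contact is needed. Cost: change is measured after 19 sessions, a modest loss when 16 of 20 counts as compliant, and practice at session 19 is still recent.

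Use the same pre-test sequence at both time points, including where the questionnaires fall. This first requires reconciling 8.1 with the schematic and 8.3.3 to 8.3.4 on where device training and the tolerability test sit relative to baseline testing.

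Recording which items are practised in session 20 would show how many tested words were rehearsed that day if the present order is kept.

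As a minor edit, reconcile the 2 hours in 5.2 (Duration of Study Participation) with the 135 minutes in 8.3.6, or 155 if the questionnaires are done within the visit, and with whichever schedule is adopted.
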